Progressive serial elevation of serum CA-125 will be used to determine CA-125 response. Guidelines for using CA-125 response have been developed and are based on the Gynecological Cancer Intergroup (GCIIG) Definitions for Response and Progression. Subjects should have a pre-treatment CA-125 of at least twice the ULN in order to be considered for CA-125 response assessment. Subjects are not evaluable by CA-125 if they have received mouse antibodies or if there has been medical and/or surgical interference with their peritoneum or pleura during the previous 28 days. In those subjects considered evaluable by CA-125, a CA-125 response would be obtained the moment the CA-125 is reduced by 50% and this should be confirmed with a consecutive CA-125 assessment not earlier than 28 days after the previous one; the date of the first 50% reduction to be the reference date for the CA-125 response.

Progression is conventionally defined according to RECIST 1.1 but can also be based on serum CA-125. In assigning the date of progression, PD by objective change in tumor size should always take precedence over CA-125 should it occur first. If measurable disease is reducing in size during treatment but the CA-125 results suggest progression, the patient should continue to receive protocol treatment. If measurable disease is stable but CA-125 indicates confirmed progression over at least 4 weeks, may advise changing protocol treatment, unless there is the possibility that the therapy could be slowing the rate of rise of CA-125. CA-125 progression is defined as:

- Elevated CA-125 pretreatment and normalisation of CA-125 must show evidence of CA-125 greater than, or equal to, two times the upper normal limit on two occasions at least one week apart or
- Patients with elevated CA-125 pretreatment, which never normalises must show evidence of CA-125 greater than, or equal to, two times the nadir value on two occasions at least one week apart or
- Patients with CA-125 in the normal range pretreatment must show evidence of CA-125 greater than, or equal to, two times the upper normal limit on two occasions at least one week apart.
- Elevated values must be confirmed by two separate measurements obtained at least one week apart. CA 125 progression will be assigned the date of the first measurement that meets the criteria as noted.

A patient may be declared to have progressive disease on the basis of either the objective RECIST criteria or the CA-125 criteria. The date of PD will be the date of the earlier of the two events if both are documented.

Sponsor: Aduro Biotech, Inc.
 Protocol Number: ADU-CL-11
 Version and Date: Version 1.0, 03MAY2018

The use of GCIG CA-125 in tandem with RECIST 1.1 in the evaluation of overall response at each visit is identified in

Table 4.

Table 4: Overall Response in Patients with Initial Measurable Disease and Evaluable by CA-125, Combining Both Criteria

| Target Lesion | Non-target Lesion | New Lesion | CA-125 | Overall Response |
|--------------------------------------|-------------------|------------|---------------|------------------|
| CR | CR | No | Normal | CR |
| CR | Non-CR Non-PD | No | Not PD | PR |
| CR | CR | No | PR not normal | PR |
| PR | Non-PD | No | Not PD | PR |
| NE | Non-PD | No | PR | PR |
| PD or New > 28 Days from CA-125 PR* | | | PR | PR |
| SD | Non-PD | No | PR | PR |
| SD | Non-PD | No | Not PR or PD | SD |
| PD or New <= 28 Days from CA-125 PR* | | | PR | PD |
| PD | Any | Yes or No | Any | PD |
| NE | PD | Yes or No | Any | PD |
| NE | Any | Yes | Any | PD |
| NE | Any | Yes or No | PD | PD |

* patients who have a CA-125 response that occurs more than 28 days from PD according to RECIST are considered a PR according to best response, but PD if the RECIST PD is within 28 days of CA-125 response

For subjects with non-measurable disease, GCIG CA-125 based overall response derivations will be conducted according to **Table 5.**

Table 5: Overall Response in Subjects without Initial Measurable Disease and Evaluable by CA-125

| CA-125 | Non-target Lesion# | New Lesion | Overall Serological Response |
|-----------------------------|--------------------|------------|------------------------------|
| Response and normalized | CR | No | CR |
| Response | Non-PD | No | PR |
| Normalized but not response | Non-CR Non-PD | No | SD |
| Non-PR Non-PD | Non-PD | No | SD |
| PD | Any | Yes or no | PD |
| Any | PD* | Yes or no | PD |
| Any | Any | Yes | PD |

#Non-target lesions include ascites and peritoneal thickening, which are not measurable according to RECIST.

*Unequivocal progression in non-target lesions may be accepted as disease progression.

Sponsor: Aduro Biotech, Inc.
Protocol Number: ADU-CL-11
Version and Date: Version 1.0, 03MAY2018

Subjects which do not have measurable disease at study entry will be evaluated based on GCIG criteria and will not be included in mRECIST and RECIST 1.1 analyses; endpoint derivations will be considered not evaluable (NE). Subjects which are not evaluable per GCIG CA-125 criteria will be handled similarly.

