14. **CA-125** will be assessed at screening as close to but no more than 14 days before the first study treatment, then on Day 1 of each cycle while on treatment (or every 3 weeks if subject dosing is delayed). Subjects who discontinue treatment for reasons other than PD should continue to have CA-125 assessed every 9 weeks until the start of a new anticancer therapy, documented PD, death, or the end of the study, whichever occurs first. Additional CA-125 time points collected per institutional standard should also be entered into the eCRF. Subjects considered CA-125 evaluable should have CA-125 repeated no earlier than 28 days if a CA-125 is reduced by 50% from baseline. See [Appendix C](#) for more details.
15. **Immune Monitoring:** Whole blood for immune monitoring will be drawn and processed into serum and plasma. Refer to the Laboratory Manual for collection and processing instructions. Samples will be sent to the central laboratory.
16. **HLA-typing:** should include type A and B of class I antigens, low resolution. HLA will be performed by the site's local laboratory.
17. **Thyroid panel:** collected at Screening, Cycle 1 Day 1, then on Day 1 of odd numbered Cycles only (Cycle 3, Cycle 5, Cycle 7, etc.) and will include: triiodothyronine (T3) or free triiodothyronine (FT3), free thyroxine (FT4), and thyroid stimulating hormone (TSH); additional thyroid function testing may be performed if clinically indicated. Blood draws may be taken up to 3 days before pembrolizumab infusion. **Additional endocrine testing for subjects receiving epacadostat:** collected at Screening, Cycle 1 Day 1, Cycle 3 Day 1 and then every 12 weeks thereafter (on Day 1 of Cycle 7, Cycle 11, Cycle 15, etc.) will include: adrenocorticotrophic hormone, serum cortisol (taken between 8-9 AM), luteinizing hormone and prolactin.
18. **Whole Blood for PBMC:** Approximately 70 mL of whole blood to be processed as described in the Laboratory Manual. PBMCs will be drawn at the following timepoints: Day 1 and Day 8 of Cycle 1, Cycle 2, Cycle 4, then Day 1 of Cycle 5, Cycle 7 and at the EOT visit.
19. **Epacadostat PK sample:** (3.5 mL) plasma for epacadostat will be taken pre epacadostat-dose on Cycle 2 Day 1. Epacadostat will be administered in clinic on Cycle 2 Day 1 in order to collect pre-dose blood sample for PK.

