5.4 Other Adverse Event Considerations

5.4.1 Dose Interruption, Modification, and Management of Events Associated with Study Treatments

In some circumstances, it may be necessary to temporarily interrupt one or more study treatments as a result of adverse events that may have an unclear relationship to study drug.

Any interruptions of >2 weeks or for LFT abnormalities must be discussed with the Study Medical Monitor before resuming treatment. Treatment with all study drugs should be withheld for drug-related Grade 4 hematologic toxicities, nonhematological toxicity \geq Grade 3 (including laboratory abnormalities), and severe or life-threatening adverse events.

Except in cases of emergency, it is recommended that the Investigator consult with the Study Medical Monitor (or other representative of the Sponsor) before temporarily interrupting therapy for reasons other than protocol-mandated medication hold. Additionally, the Investigator must notify the Study Medical Monitor and Study Project Manager via email before restarting study drug that was temporarily interrupted because of an adverse event.

Dosing interruptions may be permitted in the case of medical/surgical events or logistical reasons not related to study therapy (e.g. elective surgery, unrelated medical events, vacation, and/or holidays) upon review and approval from the Study Medical Monitor. Subjects should be placed back on study therapy within 3 weeks of the scheduled interruption, unless otherwise discussed with the sponsor. The reason for interruption should be documented in the subject's study record. Pembrolizumab may be administered up to 3 days before or after the scheduled Day 1 of each cycle due to administrative reasons. CRS-207 must be administered one day after pembrolizumab administration.

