10.2.1.1 Objective Response Rate

Objective response rate (ORR) is defined as the proportion of subjects with PR or CR according to mRECIST. Subjects who discontinue prior to post-baseline tumor assessments will be considered as non-responders.

The primary definition for objective disease response is based on mRECIST. Analyses will be performed separately using objective disease responses definitions based on the mRECIST, RECIST v1.1, and GCIG CA-125 criteria. Analysis repeated for RECIST v1.1 and GCIG CA-125 are considered supportive.

Progressive serial elevation of serum CA-125 will be used to determine CA-125 response. Guidelines for using CA-125 response have been developed. Refer to [Appendix C](#) for Gynecological Cancer Intergroup Definitions for Response and Progression Based on CA-125 Quick Reference. Subjects should have a pre-treatment CA-125 of at least twice the ULN in order

to be considered for CA-125 response. Subjects are not evaluable by CA-125 if they have received mouse antibodies or if there has been medical and/or surgical interference with their peritoneum or pleura during the previous 28 days. In those subjects considered evaluable by CA-125, a CA-125 response would be obtained the moment the CA-125 is reduced by 50% and this should be confirmed with a consecutive CA-125 assessment not earlier than 28 days after the previous one, with however the date of the first 50% reduction to be the reference date for the CA-125 response.

For each cohort in Phase 1 and each Arm in Phase 2, objective disease responses will be summarized by response at each visit and best objective response. The number of subjects with disease control, defined as subjects with best objective response of CR, PR or SD, will also be summarized.

For expansion to the second stage in Phase 2, ORR and PFS will be assessed using mRECIST as the primary measure for assessment.

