Confirmation of response	Confirmation of PR/CR is ONLY required for non-randomized trials where response is the primary endpoint. In these trials, subsequent confirmation of PR with 1 interim timepoint of SD is acceptable.
CR = complete response; CT = computed tomography; FDG-PET = positron emission tomography with fluorodeoxyglucose; LD = longest diameter; MRI = magnetic resonance imaging; PD = progressive disease; PET = positron emission tomography; PR = partial response; RECIST = Response Evaluation Criteria in Solid Tumors; SAD = short axis diameter; SD = stable disease.	

APPENDIX C: GYNECOLOGICAL CANCER INTERGROUP DEFINITIONS FOR RESPONSE AND PROGRESSION BASED ON CA-125 QUICK REFERENCE

Based on “Definitions for Response and Progression in Ovarian Cancer Clinical Trials Incorporating RECIST 1.1 and CA-125,” a set of agreements by the Gynecological Cancer Intergroup (GCIIG), the following definitions will be used in this study:

Definition of Response

“A CA-125 response is defined as at least a 50% reduction in CA-125 levels from a pretreatment sample. The response must be confirmed and maintained for at least 28 days. Patients can be evaluated according to CA-125 only if they have a pretreatment sample that is at least twice the upper limit of the reference range and within 2 weeks before starting the treatment.

“To calculate CA-125 responses accurately, the following rules apply:

- Intervening samples and the 28-day confirmatory sample must be less than or equal to (within an assay variability of 10%) the previous sample.
- Variations within the reference range of CA-125 levels will not interfere with the response definition.
- For each patient, the same assay method must be used, and the assay must be tested in a quality control scheme.
- Patients are not evaluable by CA-125 if they have received mouse antibodies (unless the assay used has been shown not to be influenced by human antimouse antibody) or if there has been medical and/or surgical interference with their peritoneum or pleura during the previous 28 days (eg, paracentesis). If assessing therapy that includes 2 treatment modalities for relapse (eg, surgery and chemotherapy), any CA-125 response results from both treatment modalities. CA-125 cannot distinguish between the effects of the 2 treatments.

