Other Concomitant Medication																
Antibiotics ²⁷												X				

Footnotes

1. Treatment will continue for 6 cycles as long as there is potential for clinical benefit. After 6 cycles, treatment may continue if there is continued potential benefit and upon approval from the Study Medical Monitor. After Cycle 3 Day 8, visits between administrations of CRS-207 will be conducted based on Investigator's discretion. After Cycle 3 Day 1, initiation of a new cycle may be delayed up to 3 days due to subject scheduling. Epacadostat should continue uninterrupted during the treatment period.
2. An EOT Visit will occur as soon as determined that the subject will permanently discontinue study treatment, and at least 7 days after the last dose of CRS-207. If the EOT visit coincides with a regular study visit, the EOT evaluations will supersede those of that scheduled visit, and the data should be entered in the EOT page in the eCRF. If the EOT Visit occurs >21 days after the last administration of study drug, procedures from the EOT and Safety Follow-up visits may be collected as a single Safety Follow-up Visit.
3. A Safety Follow-up Visit will be scheduled 30 days (+5 days) post last dose of study treatment. If the subject begins another anticancer therapy before the Safety Follow-up Visit, every effort will be made to complete all of the Safety Follow-up Visit assessments prior to commencing the new therapy. If there is an adverse event in need of

monitoring beyond the Safety Follow-up Visit, the subject will be followed until resolution or confirmed stability of the adverse event. If a CT scan was collected within 9 weeks (± 7 days) of the Safety Follow-up Visit, then a CT scan at the Safety Follow-up Visit will not be mandatory.

4. For Phase 1, enrollment form will be completed and sent to Medpace for treatment assignment. As an added safety measure during Phase 1, Dose Cohort 1 will have a staggered enrollment of no more than 1 new subject treated per week during the dose escalation phase. Thereafter, a decision to further stagger combination enrollment will be made by the SRC and will be based on emergent safety data.
5. Vital sign measurements consist of seated BP, pulse, respiratory rate, and temperature. Pulse oximetry will be measured if clinically indicated. Weight will be taken on Day 1 of each cycle. Height is required at screening only.

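### The CA-125 response confirmation rule in SAP section 7 and Protocol 10.2.1.1 does not match Appendix C: read literally it fails adjacent on-treatment samples, read loosely it lets a transient fall count

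*SAP*

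**What the plan says.** SAP section 7 defines a CA-125 response as a 50% reduction, "confirmed with a consecutive CA-125 assessment not earlier than 28 days after the previous one", and dates it to the first 50% reduction. Protocol 10.2.1.1 has the same sentence: "this should be confirmed with a consecutive CA-125 assessment not earlier than 28 days after the previous one". The SAP describes its rule as based on the GCIG definitions.

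The sampling schedule is the same in both phases (Table 1 footnote 14; Appendix F footnote 14). CA-125 is drawn at screening, "then on Day 1 of each cycle while on treatment (or every 3 weeks if subject dosing is delayed"). Both footnotes and Protocol 8.2 add a response-triggered draw: "Subjects considered CA-125 evaluable should have CA-125 repeated no earlier than 28 days if a CA-125 is reduced by 50% from baseline". Subjects who stop treatment for reasons other than progression are sampled every 9 weeks (±7 days in Protocol 8.2).

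Appendix C, which states that its definitions apply in this study, does not require the confirming sample to be the next one. It says "The response must be confirmed and maintained for at least 28 days" and adds "Intervening samples and the 28-day confirmatory sample must be less than or equal to (within an assay variability of 10%) the previous sample".

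**The concern.** The sentence joins two conditions that the on-treatment schedule does not deliver together: the confirming sample is to be *consecutive*, and it is to come at least 28 days after the one before. With draws every 21 days, the next routine sample is too early and a late enough sample is not the next one. A programmer must therefore drop one of the conditions, and the SAP does not say which.

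The choice matters because CA-125 response feeds the GCIG overall response. In SAP Table 4, stable disease by RECIST plus a CA-125 PR becomes an overall PR. In Table 5, CA-125 response is the route to CR or PR for subjects without measurable disease, who can enter Phase 1 only and whom the SAP evaluates by GCIG alone. GCIG-based ORR and duration of response are secondary endpoints in both phases. The literal choice rejects sustained on-treatment responses in fully sampled subjects. It can accept the same response in a subject who missed a draw, so responder status would depend on missing data. The loose choice can accept falls that were not sustained.

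**Working it through.** The plan gives no figure of its own for this rule, so the check is interval arithmetic on the schedule.

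**Inputs**
- Cycle length: 21 days (Protocol section 3).
- Phase 2 Day 1 window: ±3 days from Cycle 2 on (Table 1 window row). Protocol 5.4.1 agrees: "Pembrolizumab may be administered up to 3 days before or after the scheduled Day 1 of each cycle due to administrative reasons". Cycle 1 Day 1 has no window.
- Phase 1: no window on Day 1, but after Cycle 3 Day 1 "initiation of a new cycle may be delayed up to 3 days due to subject scheduling" (Appendix F footnote 1).
- Off treatment: 63 days, ±7 at each visit.
- Required minimum: 28 days.
- Assumption: CA-125 is drawn at the Day 1 visit, within that visit's window.

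**Formula.** The gap over k cycles is 21k days, ±(3 + 3) when both Phase 2 visits use the window.

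| Pair of samples | Nominal (days) | Range (days) | Reaches 28? |
|---|---|---|---|
| Phase 2, next Day 1 | 21 | 21 − 6 = 15 to 21 + 6 = 27 | Never |
| Phase 2, Cycle 1 Day 1 to Cycle 2 Day 1 | 21 | 21 − 3 = 18 to 21 + 3 = 24 | Never |
| Phase 1, next Day 1 | 21 | 21 to 21 + 3 = 24 | Never |
| Phase 2, Day 1 two cycles later | 42 | 42 − 6 = 36 to 42 + 6 = 48 | Always |
| Phase 1, Day 1 two cycles later | 42 | 42 to 42 + 2×3 = 48 | Always |
| Two off-treatment samples | 63 | 63 − 14 = 49 to 63 + 14 = 77 | Always |

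If the Phase 2 window runs from the previous actual visit instead of from Cycle 1 Day 1, the longest gap to the next sample is 21 + 3 = 24 days. The two-cycle range is 2×18 = 36 to 2×24 = 48. The conclusion is the same.

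**The response-triggered repeat.** The instruction does not replace the next Day 1 draw, nominally at day 21. A repeat at day 28 is then the second sample after the fall and comes 28 − 21 = 7 days after the one before it. Under the literal reading it is neither the next sample nor 28 days after its predecessor. Extra institutional samples, which must also go into the eCRF, shorten adjacent gaps further.

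**The loose reading.** Suppose the first qualifying value is 50% of pretreatment. Appendix C then allows the next sample to be at most 50% × 1.10 = 55% of pretreatment. A day-21 value above 55% breaks the response under Appendix C (leaving aside its exemption for variation within the reference range). The SAP sentence has no such check, so a return to 50% or below at day 42 would confirm the response.

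**Response tables side by side.** Both best-response tables in Appendix C carry a column requiring confirmation and maintenance for at least 28 days. SAP Tables 4 and 5 reproduce the rows without that column. The loss bears most directly on Table 5, where the column governs the serological response. In the measurable-disease table it is worded for the RECIST response. The section 7 sentence is thus the only CA-125 response confirmation rule that the SAP states.

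**The case against.** The strongest reply is that the documents, read together, already give the answer. Appendix C declares that its definitions will be used, and Protocol 10.2.1.1 refers to it in the same paragraph as the criticised sentence. The SAP says its rule is based on GCIG and cites the GCIG paper, and its section on changes to the planned analysis revokes nothing. Appendix C plainly expects intervening samples, so *consecutive* cannot sensibly mean the adjacent one. The protocol also orders a draw at 28 days or later for this very purpose.

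Much of this stands. A reader might infer from the 27-day maximum that scheduled sampling can never confirm a CA-125 response. The documents do not support that. The repeat draw is part of the plan, the Day 1 sample two cycles later is always late enough once intervening samples are allowed, and off-treatment samples meet even the literal rule. The 27-day figure is also a Phase 2 maximum only, and the wording originates in the protocol, so this is not an error of the SAP alone.

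What does not stand is that nothing needs changing. Derivations are programmed from the SAP. Section 7 keeps the word that Appendix C lacks, omits the check that Appendix C has, and does not send the reader to Appendix C for the response rule.

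**Conclusion.** The point holds as a conflict of wording that should be corrected. It is not a schedule that makes confirmation impossible. Under the literal reading, none of the adjacent on-schedule on-treatment pairs reaches 28 days (maximum 27 in Phase 2, 24 in Phase 1). Under the loose reading, confirmation is available at 36 to 48 days, but at least one intervening sample goes unchecked when sampling is on schedule.

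The consequence is limited. It reaches GCIG-based best overall response, duration of response, and Phase 1 subjects without measurable disease. Disease control is less sensitive, since a rejected response will often fall back to SD. GCIG-based PFS could be touched only indirectly, through the Table 4 rows where a CA-125 PR alters how a RECIST progression is classified; CA-125 progression has its own confirmation rule. Protocol 10.2.1.1 calls the GCIG analyses supportive, stage decisions use mRECIST, and SAP section 9 says efficacy is listed without summaries. CA-125 results are listed too, so a derived response can be checked by hand. How many subjects would change status cannot be known from the documents.

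The result rests on CA-125 being drawn within the Day 1 window, and on the repeat being additional to the routine draw.

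**What to change.** In SAP section 7, replace the confirmation sentence with Appendix C's rule:

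- a fall of at least 50% from the pretreatment sample;
- confirmed by a later sample at least 28 days after the first qualifying sample, not necessarily the next one;
- every intervening sample and the confirmatory sample no higher than the one before, within 10%;
- response dated to the first 50% reduction.

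Carry the 28-day confirmation requirement into the notes to SAP Tables 4 and 5. State in the SAP that the matching sentence in Protocol 10.2.1.1 is to be read by reference to Appendix C. Development has ceased and the SAP serves a synopsis report, so a separate protocol amendment seems unnecessary.

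The cost is a few lines of text and a small programming change. It uses samples already collected.
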